	References	32

DEFINITIONS

Adverse event (AE) – any undesirable patient experience that may include but is not limited to an abnormal sign, symptom, illness, abnormal laboratory value, or other medical event.

ADAS-Cog 13 - an outcome measure for global cognition in clinical trials for Alzheimer's Disease.

Amnesic Mild Cognitive Impairment (aMCI) - A condition characterized by subject memory complaints and objective neuropsychological testing demonstrating abnormalities >1.0 SD affecting memory. There is preservation of instrumental activities of daily living without functional limitations. This population has a 40% chance of developing Alzheimer's Disease over a 2 year period.

Alberta Smell Test (AST) - A test to identify the olfactory abilities of an individual.

Alzheimer's disease (AD) – A chronic progressive neurodegenerative condition resulting in memory impairment, loss of function, and progressive deterioration in other cognitive domains including language, perceptual skills, attention, construction, orientation, and problem solving.

Animal Naming - a word fluency test measuring executive functioning and language ability.

Mild Alzheimer's disease - Patients meeting NINCDS-ADRDA criteria for probable AD with a CDR=1

Columbia-Suicide Severity Rating Scale (C-SSRS) - A scale designed to quantify the severity of suicidal ideation and behavior.

Controlled Oral Word Association Test (COWAT) - a short, paper/pencil measure of phonemic fluency and executive functioning from the Multilingual Aphasia Examination.

Clinical Dementia Rating (CDR) - a numeric scale used to quantify the severity of symptoms of dementia (i.e. stage).

Data Safety Monitoring Board (DSMB) - an independent group assigned to review safety data to monitor for incidence of trends that would warrant termination of the trial.

Diagnostics and Statistical Manual-IV(DSM-IV TR) – a diagnostic manual published by the American Psychiatric Association that provides a common language and standard criteria for the classification of mental disorders including Alzheimer's Disease.

Digit Span subtest from the Wechsler Adult Intelligence Scale -4th Edition (WAIS-IV) - is a brief measure of auditory attention, concentration, and working memory.

Epworth Sleepiness Scale (ESS) – A measure to identify excessive daytime sleepiness.

Geriatric Depression Scale (GDS) - a screening test for depression in older adults.

Glulisine - a rapidly absorbed insulin analogue lacking the zinc ingredient commonly found in insulin formulations and characterized by a unique amino acid sequence that distinguishes it from other commercially available insulin compounds.

The Functional Activities Questionnaires (FAQ) – a measure of instrumental activities of daily living (IADLs).

Hachinski Ischemia Score - a screening tool used to differentiate vascular causes of dementia from neurodegenerative causes. A score of ≥ 7 is suggestive of a vascular etiology.

Intranasal (IN) - a method of drug delivery that is particularly applicable to conveying centrally acting medications into the central nervous system.

Mini Mental State Exam (MMSE) - a 30 point cognitive screening tool that assesses orientation, working memory, short term memory, visuospatial construction, and language.

Montreal Cognitive Assessment (MOCA) - a 30 point screening instrument for cognitive impairment that has a 90% sensitivity for MCI and 100% sensitivity for AD.

National Institute of Neurological and Communicative Disorders and Stroke and the Alzheimer's disease and Related Disorders Association (NINCDS-ADRDA) criteria - criteria used to diagnose definite, probable, possible and unlikely Alzheimer's disease for research and clinical purposes. These criteria specify eight cognitive domains that may be impaired in AD: memory, language, perceptual skills, attention, constructive abilities, orientation, problem solving and functional abilities. These require that symptoms are confirmed by neuropsychological testing or screening in probable AD.

Trail Making Test, Parts A & B - a brief paper and pencil measure of attention, processing speed, and mental flexibility (or set-shifting).

Serious adverse events (SAE) - any symptom, sign, illness or experience that develops during the study and results in a life-threatening situation, hospitalization, significant disability, and other events determined by the investigator to be significant.

WMB Logical Memory - The Wechsler Memory Scale (WMS) is a neuropsychological test designed to measure different memory functions.

PROTOCOL SUMMARY

PROTOCOL TITLE	A Phase II, Single Center, Randomized, Double-Blind, Placebo-Controlled Study of the Safety and the Therapeutic Effectiveness of Intranasal Glulisine in Amnesic Mild Cognitive Impairment and Probable Mild Alzheimer's Disease.	
SHORT TITLE	MCI-AD IN Insulin Study	
STUDY PHASE	Phase II	
STUDY OBJECTIVES AND PURPOSE		
Primary Objective: To measure the chronic effects of IN insulin glulisine on cognition and function in subjects with aMCI and probable mild AD over a 6 month period.		
Secondary Objectives:		

 To measure the effect of IN insulin glulisine on mood in subjects with aMCI and mild AD over a 6 month period. To measure the safety and efficacy of IN glulisine in aMCI and mild AD subjects with non-insulin dependent diabetes over a 6 month period. 		
Exploratory Objectives:		

 To measure the effect of IN delivery of insulin glulisine on parieto-temporal and posterior cingulate/precuneus glucose metabolism in subjects with aMCI and mild AD over a 6 month period. To measure the chronic effect of IN delivery of insulin glulisine on AD-specific cerebrospinal (CSF) biomarkers (Abeta42, tau, and phosphotau) in subjects with aMCI and mild AD over a 6 month period. To measure the chronic effect of IN delivery of insulin glulisine on sleep in subjects with aMCI and mild AD over a 6 month period. To measure the chronic effect of IN delivery of insulin glulisine on olfaction in subjects with aMCI and mild AD over a 6 month period. 		
STUDY DESIGN		
Study Type	Safety	
Control Type	Placebo	
Study Indication Type	Treatment	
Blinding Schema	Double-Blind	
Device	Pressurized Olfactory Delivery (POD) device	
Study Design	Randomized, double-blinded control	
Planned Duration of Subject Participation	8 months	
ENDPOINTS	Primary	
 ADAS-Cog 13 CDR-SOB FAQ
	Secondary	
 Digit Span Forward

		
 • Trailmaking Test Parts A&B • Controlled Oral Word Association Test (COWAT) • Animal Naming • Weschler Memory Scale (WMS) • Geriatric Depression Scale (GDS)
	Exploratory	
 • CSF Abeta, tau, phosphotau • FDG-PET metabolism posterior parietotemporal, posterior cingulate, and precuneus regions • Sleep questionnaire/Epworth Sleepiness Scale (ESS) • Alberta Smell Test
INVESTIGATIONAL PRODUCTS, DOSE AND MODE OF ADMINISTRATION		
Investigational Product	Glulisine 20 IU/IN (.1ml/10 units IN in each nostril) BID	
Placebo	Sterile Normal Saline 20 IU/IN placebo (.1ml IN in each nostril) BID	
SUBJECT SELECTION		
Targeted Accrual	Approximately 90 randomized subjects. We estimate will need to consent 130 participants in order to reach this goal.	
Inclusion Criteria 
 1. Male or female subject with a clinical and research diagnosis of amnesic-mild cognitive impairment (1, 2) OR probable mild AD in accordance with NINCDS-ADRDA criteria (3) 2. Subject has a MOCA score of 18-27. 3. Subject has a Hachinski Ischemia Score ≤ 4. 4. Subject is ≥ 50 and <90 years of age. 5. Female subjects must be at least 2 years post-menopausal or surgically sterile. 6. The subject must be proficient in speaking, reading and understanding English in order to comply with procedural testing of cognitive function, memory and physiology. 7. Subject has a dedicated family member /caregiver, who will be able to attend all visits and report on subject's status. 8. Subject and family member/caregiver have both provided fully informed written consent prior to participation. In the event that subject is legally unable to provide informed written consent due to deterioration in cognitive abilities, fully informed written consent must be provided by a legally authorized representative. 9. If AD, subject must have a brain CT or MRI in the initial diagnostic work up or subsequent care that is compatible with the diagnosis of probable Alzheimer's Disease. 		
Exclusion Criteria 
 1. Subject has medical history and/or clinically determined evidence of other CNS disorders including, but not limited to brain tumor, active subdural hematoma, seizure disorder, multiple sclerosis, dementia with Lewy bodies, vascular dementia, corticobasal syndrome, progressive supranuclear palsy, Parkinson's disease, multiple system atrophy, frontotemporal dementia, normal pressure hydrocephalus, Huntington's disease, or Jakob-Creutzfeldt disease 		

presenting as dementia.

2. Subject has medical history and/or clinically determined disorders: current B12 deficiency, chronic sinusitis or any untreated thyroid disease, significant head trauma, or history of difficulty with smell and/or taste prior to AD diagnosis.
3. Subject has history of any of the following: moderate to severe pulmonary disease, poorly controlled congestive heart failure, significant cardiovascular and/or cerebrovascular events within previous 6 months, condition known to affect absorption, distribution, metabolism, or excretion of drugs such as any hepatic, renal or gastrointestinal disease or any other clinically relevant abnormality that inclusion would pose a safety risk to the subject as determined by Investigator.
4. Subject has had previous nasal and/or oto-pharyngeal surgery and severe deviated septum and/or other anomalies.
5. Subject has history of any psychiatric illness, with the exception of major depressive and anxiety disorder (according to DSM-IV TR) currently in remission or stable with treatment for ≥ 2 years, or any other psychiatric condition that inclusion would pose a safety risk to the subject as determined by investigator.
6. Subject is currently taking any medications, herbals and food supplements that are medically/clinically contraindicated as determined by investigator in order to comply with procedural testing of cognitive function as well as ensure study safety. See list of prohibited medications and compounds.
7. Subject has undergone a recent change (≤ 1 month) in their prescribed acetylcholinesterase inhibitor (e.g. donepezil, rivastigmine, galantamine) or memantine.
8. Subject has undergone a recent change (< 1 month) in their SSRI or anti-depressant medication.
9. Subject has current or recent drug or alcohol abuse or dependence as defined by DSM-IV TR.
10. Screening laboratory results that are medically relevant, in which inclusion would pose a safety risk to the subject as determined by investigator.
11. The subject has participated in any other research study at least 3 months prior to this study.
12. The subject has an insulin allergy.

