6.1.2. Exclusion Criteria

A subject will *not* be included for consideration in this study if any of the following criteria are met:

1. Subject has medical history and/or clinically determined evidence of other CNS disorders including, but not limited to brain tumor, active subdural hematoma, seizure disorder, multiple sclerosis, dementia with Lewy bodies, vascular dementia, corticobasal syndrome, progressive supranuclear palsy, Parkinson's disease, multiple system atrophy, frontotemporal dementia, normal pressure hydrocephalus, Huntington's disease, or Jakob-Creutzfeldt disease presenting as dementia.
2. Subject has medical history and/or clinically determined disorders: current B12 deficiency, chronic sinusitis or any untreated thyroid disease, significant head trauma, or history of difficulty with smell and/or taste prior to AD diagnosis.
3. Subject has history of any of the following: moderate to severe pulmonary disease, poorly

controlled congestive heart failure, significant cardiovascular and/or cerebrovascular events within previous 6 months, condition known to affect absorption, distribution, metabolism, or excretion of drugs such as any hepatic, renal or gastrointestinal disease or any other clinically relevant abnormality that inclusion, would pose a safety risk to the subject as determined by investigator.

4. Subject has had previous nasal and/or oto-pharyngeal surgery and severe deviated septum and/or other anomalies.
5. Subject has history of any psychiatric illness, with the exception of major depressive and anxiety disorder (according to DSM-IV TR) currently in remission or stable with treatment for ≥ 2 years, or any other psychiatric condition that inclusion would pose a safety risk to the subject as determined by investigator.
6. Subject is currently taking any medications, herbals and food supplements that are medically/clinically contraindicated as determined by investigator in order to comply with procedural testing of cognitive function as well as ensure study safety. See list of prohibited medications and compounds.
7. Subject has undergone a recent change (≤ 1 month) in their prescribed acetylcholinesterase inhibitor (e.g. donepezil, rivastigmine, galantamine) or memantine.
8. Subject has undergone a recent change (< 1 month) in their SSRI or anti-depressant medication.
9. Subject has current or recent drug or alcohol abuse or dependence as defined by DSM-IV TR.

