10. Screening laboratory results that are medically relevant, in which inclusion would pose a safety risk to the subject as determined by investigator.
11. The subject has participated in any other research study at least 3 months prior to
12. The subject has an insulin allergy.

1. Study assessments and procedures

A summary of study events and procedures is outlined in the Study Visit Table. Demographic, Screening, and Baseline Assessments are described in Sections 7.1.1-7.1.2, the Treatment Phase is outlined in Sections 7.1.3-7.1.10, and the Safety monitoring are detailed in Section 7.1.11; details of neuropsychological assessments are outlined in Section 7.4. Note that all visits are non-fasting unless otherwise noted.

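### Exclusion criterion 11 points the wrong way: it excludes participation in another study 3 or more months ago and does not exclude participation confined to the last 3 months

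*Combined protocol and SAP*

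**What the plan says.** The Protocol Summary lists as exclusion 11: "The subject has participated in any other research study at least 3 months prior to this study". Section 6.1.2 repeats the item as far as "The subject has participated in any other research study at least 3 months prior to", where the sentence breaks off. The break may come from how the text was extracted and is not held against the plan; the direction of the interval is already clear before it.

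The lead-in to Section 6.1.2 says that a subject will not be "included for consideration in this study if any of the following criteria are met". Item 11 is therefore a reason to keep someone out, not a condition they must satisfy.

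Other exclusions aimed at recent exposure look back over a recent window. Item 3 refers to "significant cardiovascular and/or cerebrovascular events within previous 6 months". Item 7 reads "Subject has undergone a recent change (≤ 1 month) in their prescribed acetylcholinesterase inhibitor", and item 8 applies a limit of less than 1 month to antidepressant changes.

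**The concern.** A rule of this kind normally keeps out people who are in another study or have only just left one. Item 11 attaches its 3-month limit to the other side. The phrase would fit a requirement to have been free of other studies for that long, but it has been placed in a list of reasons to exclude.

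The primary outcomes are changes from baseline in ADAS-Cog 13, CDR-SOB and FAQ (Sections 4.1 and 12.2). A recent investigational treatment, or recent practice on the same or similar cognitive tests, can shift both the baseline score and the later change. Under the literal rule those people are not stopped by item 11, while people with only old participation are refused without an evident reason. Prior research participation is a realistic prospect here: Section 1.1 describes an earlier glulisine pilot with cognitive testing, run by the same centre.

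**Working it through.** No formula applies, and the plan gives no figure to reproduce. The check is logical: apply item 11 as written, then as a look-back rule, to each pattern of participation, and see where the results differ.

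- Literal rule: exclude if any participation took place 3 or more months before this study.
- Look-back rule: exclude if any participation took place within the 3 months before this study, or is current.

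| Participation in other studies | Literal item 11 | Look-back rule | Same result? |
|---|---|---|---|
| None | Not excluded | Not excluded | Yes |
| Only participation was over 3 or more months ago | Excluded | Not excluded | **No** |
| Only participation began and ended within the last 3 months | Not excluded | Excluded | **No** |
| Current study, joined less than 3 months ago, nothing earlier | Not excluded | Excluded | **No** |
| Current study, joined 3 or more months ago | Excluded | Excluded | Yes |
| Began 3 or more months ago, ended within the last 3 months | Excluded | Excluded | Yes |
| Both an old and a recent study | Excluded | Excluded | Yes |

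The two rules give opposite results in three patterns and agree in the other four.

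Next, does anything else in the plan cover the two patterns that the literal rule lets through?

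- Exclusion 6 begins "Subject is currently taking any medications, herbals and food supplements that are medically/clinically contraindicated as determined by investigator". It is discretionary and concerns medications and supplements, not research participation.
- The prohibited-medication list in Section 9 names drug classes. It does not mention investigational agents, and Section 9.1 permits whatever is not listed as prohibited or conditional.
- The screening visit (Section 7.1.1) collects medications for the previous 30 days. An investigational agent stopped after that point but inside 3 months, roughly 31 to 90 days earlier, might not be recorded.
- The withdrawal reasons in Section 10.2 do not name participation in another study.

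Item 11 is thus the only rule on the subject. The provisions above may catch some concurrent drug exposure, but they are not a substitute for a washout.

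**The case against.** The strongest reply is that this is a drafting slip that few people would follow to the letter. Every neighbouring window targets recent exposure, so an experienced coordinator would probably read item 11 as covering the last 3 months. The trial has a single centre, so different sites cannot diverge, and nothing in the documents shows the rule being applied in reverse. This is fair as to the likely harm. It does not rescue the text: a screener must still choose between the words and the presumed intent, and either choice can be recorded as a deviation.

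A second reply is that eligibility is settled before random allocation in a double-blind trial, so residual exposure or practice effects are expected equally in both arms, and the primary model adjusts for baseline scores. This also stands. A reader might infer that the treatment comparison is biased; the design does not support that. What remains is possible extra variability, since baseline adjustment need not remove an effect on change.

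A reader might also infer that the rule is inverted for everyone with a research history, or that it lets in anyone now in another study. The table shows otherwise: people with both old and recent participation, and people in a concurrent study joined 3 or more months ago, are excluded under either reading. Nor does passing item 11 amount to admission, because exclusion 6 or the medication list could still keep a person out.

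**Conclusion.** The point holds as a wording error in an operative eligibility rule, with the same direction in both lists. Followed literally, it gives the wrong result for people whose only participation is over and 3 or more months old, and for people whose only participation lies within the last 3 months, concurrent or not. No other provision fills the gap.

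Its effect is modest. The plausible consequences are noise in baseline and change scores, needless refusal of some candidates, and screening decisions that cannot be audited against the text. The power table in Section 12.4 and the two-sided 0.05 level do not depend on this item, and no between-arm imbalance is expected from it. A reader might want to turn the planned 130 consents into a count of people misclassified. The documents give no share with prior participation and no indication of how staff apply the rule, so no such figure is supported.

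The conclusion assumes that the intent was a washout. The document does not say so; the inference rests on the neighbouring look-back criteria.

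**What to change.** Reword item 11 identically in the Protocol Summary and Section 6.1.2. It should exclude a person who is currently taking part in any other research study or who has taken part in one within the 3 months before this study. The status of current participation should be written out and not left to inference. It would also help to name the event from which the 3 months are counted back.

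Keep the present scope, which covers research studies of any kind. Limiting the rule to interventional studies would be a separate decision for the sponsor. It would allow recent observational studies that use the same cognitive tests, and so would leave the practice-effect concern open.

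The cost is a wording amendment in two places and a matching update to any screening checklist. No analysis, sample size or visit schedule changes. If screening has already begun, a short note recording how item 11 has been applied so far would let decisions already made be checked.

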1. INTRODUCTION

1.1 Background and Rationale

Alzheimer's disease (AD) is the most common cause of dementia, representing 60-80% of all cases and afflicting 5.4 million individuals within the United States. While characteristic amyloid plaques (AP) and neurofibrillary tangles (NFT) represent the pathognomic signature of AD, the AD brain is characterized by a severe impairment of insulin-signaling, including deficits of insulin, insulin-like growth factor, insulin receptors as well as central resistance to insulin action (4-8). Disruption of central nervous system (CNS) insulin signaling has been increasingly associated with AD pathogenesis, and consequently this disease has been referred to as a type III diabetes of the brain (9). Furthermore, longitudinal cohort studies have shown that diabetes doubles the risk of AD (10) and have linked high blood sugar with increased dementia risk (11). Fluorodeoxyglucose positive emission tomography (FDG-PET) studies of subjects with peripheral insulin resistance demonstrate a cerebral pattern of frontal, parietotemporal, and cingulate cortical hypometabolism that mimics AD (12).

Originally thought to exist solely in the periphery, insulin has since been determined to be instrumental in the overall health and function of the CNS (13). Central insulin and insulin receptors (IRs) have been established as differing from that of the systemically occurring counterparts that specifically regulate glucose utilization. Although central insulin does induce glucose uptake in the brain, it also functions in the modulation of various neurotransmitters and receptors involved in executive function and the long-term potentiation of memories. For example, systems with impaired insulin signaling pathways have demonstrated inhibition of acetylcholine biosynthesis and subsequently have incurred debilitating effects on neuronal plasticity (7, 14). Consistent with evidence of insulin functioning as a neuromodulator for memory-related function is the high-density of IRs in the hippocampus and cerebral cortex, brain regions integral to the formation, retention and recall of information (13, 15).

Brain deposition of beta-amyloid ($A\beta$) plaques and neurofibrillary tangles (NFTs) are both critical pathological signatures of AD, but are also modulated by CNS insulin activity. Increased insulin concentration upregulates the production of insulin-degrading enzyme (IDE); a multifunctional enzyme that removes soluble $A\beta$ and promotes intracellular $A\beta$ degradation (5). As AD progresses, the presence of soluble $A\beta$ aggregates further induces tau hyperphosphorylation as well as decreases the number of synaptic insulin receptors (IRs) (5). The downregulation of dendritic surface IRs from accumulating $A\beta$ compromises synaptic function in brain regions associated with memory and cognitive function, leading to the disruption in the insulin-signaling pathway that is characteristic of AD (16). Insulin further inhibits neurofibrillary tangle production by maintaining a phosphorylation equilibrium between kinase and phosphatase activity (8, 17-19).

Intranasal (IN) delivery offers a non-invasive route to deliver large molecules such as insulin directly to the brain while minimizing systemic exposure. Peptides, proteins, vaccines, drug treatments and ions of various sizes are able to pass along the olfactory and trigeminal nerves and are deposited directly into the CNS without having to pass through the BBB that may degrade or limit the amount arriving at the target (20-27). Increased insulin in healthy adults has been detected in CSF as soon as 10 minutes after IN delivery while not measurably increasing

systemic blood-glucose levels (22, 28). Similar effects have been achieved using IN insulin with human subjects of altered brain insulin concentrations (29, 30).

Clinical trials of intranasal insulin in AD have demonstrated therapeutic effects involving memory, attention and cognition without significantly altering serum insulin or glucose levels. A clinical trial consisting of 26 memory impaired subjects (13 with AD and 13 with mild cognitive impairment) and 35 normal controls showed that IN insulin 20 IU or 40 IU resulted in improvements on two declarative memory tasks compared to placebo within 15 minutes of drug administration (29). IN insulin administered at 20 IU resulted in greater story recall whereas doses at 40 IU more favorably improved word list recall. There was no impact on IN insulin on serum glucose or insulin levels. Another study of 24 early AD/mild cognitive impairment subjects showed that 20 IU BID of intranasal insulin resulted in sustained benefit in over a 21 day period (30). Furthermore, IN insulin induced favorable changes in the serum amyloid-beta 40/42 ratio while having no impact on systemic glucose or insulin levels. Most recently, Craft and colleagues have shown improved memory and function as represented by the ADAS-Cog and ADCS-ADL, respectively in AD patients treated during a four month clinical trial (31). These changes in memory and function were associated with favorable changes in CSF tau and tau-Ab42 ratio. Additionally, IN insulin minimized progression in loss of cerebral hypometabolism as measured by FDG-PET.

Therapeutic response to IN insulin may be modified by both insulin type as well as ApoE4 carrier status. A study of 38 normal subjects showed that rapid-acting insulin aspart (Insulin NovoLog HM, Novo Nordisk) resulted in greater declarative memory improvements compared to regular insulin over 8 an week period (32). Additional clinical trials have suggested memory benefits associated with IN insulin are diminished among ApoE4 carriers diagnosed with AD (29).

Glulisine is a rapidly absorbed insulin analogue lacking the zinc ingredient commonly found in insulin formulations. This analogue differs from human insulin in that the amino acid asparagine at position B3 is replaced by lysine and the lysine in position B29 is replaced by glutamic acid. For this study, we have chosen glulisine due to prior speculation that zinc-containing compounds may be toxic to olfactory neurons (33, 34) as well as prior studies demonstrating improvements in declarative memory with RA compared to regular insulin.

To test the hypothesis regarding the acute safety and efficacy of glulisine, the HealthPartners Center for Memory and Aging performed a double blinded, randomized, placebo-controlled, cross-over pilot study in 9 subjects with mild-moderate AD. We further sought to address the responsiveness of ApoE4 carriers to this treatment, and so all subjects were carriers of this polymorphism. The study drug was intranasally administered using the LMA Mucosal Atomization Device (MAD) and was not associated with any serious adverse events. Treated subjects made fewer Trails B errors relative to controls. Otherwise, there were no significant difference between IN glulisine and placebo for cognitive tests of learning/memory, attention/executive function, language, or visuospatial function. Fingertick glucose was not impacted by IN glulisine, but the drug resulted in a 19% decrease in insulin levels compared to placebo. The conclusion was that ApoE4 subjects were unresponsive to acute IN glulisine, but the drug was safe and well-tolerated.

In the current study, we are investigating the chronic effects of IN glulisine 20 IU administered two times daily in adults with amnesic-mild cognitive impairment (a-MCI) and mild Alzheimer's disease (AD). The investigation will enroll n=90 subjects and follow them over a 6 month period. This study is characterized by three major changes: 1.) the IN glulisine will be administered using the Pressurized Olfactory Delivery (POD) Device; 2.) the study will include non-insulin dependent diabetics; 3.) the study will incorporate biomarkers for amyloidosis (cerebrospinal fluid Abeta42) and neurodegeneration (cerebrospinal tau/phosphotau and FDG-PET).

In the acute pilot study, we had employed the LMA MAD device in the acute setting, but for this chronic trial, there is concern about variable, user-dependent drug delivery due to dependency upon subject positioning and inconsistent volume ejection. The POD device is more practical for a 6 month clinical trial. The POD device is powered with a standard hydrofluoroalkane (HFA) meter valve to administer drug into the nasal cavity rather than the mechanical ability of the user, which results in greater inter-user consistency.

This study will also include a subsample of subjects with non-insulin dependent diabetes. Studies have shown that diabetics have twice the risk of Alzheimer's disease (35) and FDG-PET scans demonstrate a pattern of hypometabolism resembling Alzheimer's disease (12). We hypothesize that the subjects with peripheral deficits in insulin signaling will also be the ones to demonstrate deficits in central nervous system signaling. While diabetics comprise a significant portion of patients with AD, previous studies have excluded this population due to concerns regarding hypoglycemia in the setting of concomitant oral hypoglycemics or intranasal insulin. However, studies in non-diabetic subjects have failed to reveal any significant glucose lowering effects of IN insulin. There are minimal investigations addressing the effect of intranasal insulin on peripheral glucose in non-insulin dependent diabetes. One of the secondary objectives of this clinical trial is to demonstrate the safety and efficacy of IN glulisine in this population. Based on the multiple trials failing to reveal effects on peripheral glucose, we suspect that IN insulin will be well-tolerated in this population.

Finally, investigations have shown that Alzheimer's disease is characterized by the co-existence of cerebral amyloidosis with neurodegeneration, and that biomarkers of these abnormal changes can be used to support an AD diagnosis as well as longitudinally track disease progression (36). Most recent AD clinical trials have included biomarkers from CSF and FDG-PET to provide evidence for biological drug actions related to amyloidosis and neurodegeneration (37, 38).

2. Summary of Device Description

